We propose that daily locomotor training in the presence of SCES will enable the individual with clinically complete SCI to stand and step independently while bearing full weight. Non-patterned electrical stimulation of the lumbar spinal cord can induce patterned, locomotor-like activity in individuals with clinically complete SCI [1]. Modifying the frequency of stimulation can induce extensor patterns similar to that observed during standing [45]. In addition, when afferent information is also provided there is further modulation of these motor patterns elicited by epidural stimulation [46]. Individuals with a clinically complete spinal cord injury can execute independent steps using a body weight support system on a treadmill (BWST) using manual assistance without epidural stimulation. When combined with SCES, we anticipate the training will be even more successful, enabling prolonged periods of independent stepping and standing. Although there will not be a separate control group studied simultaneously, historical controls will consist of the best stepping and standing performance that have been observed previously in our laboratory in individuals that have a clinically complete SCI. Performance beyond this threshold by any individual treated with both epidural stimulation and training will be interpreted as a significantly better intervention than training alone.

Future studies will eventually focus on development and implementation of the more advanced multi-electrode array technique that will provide functionally-adaptive site-specific stimulation. The adaptive stimulation strategy proposed here takes advantage of capabilities of our new array design that are not possible using either conventional or commercially available electrode arrays. Our future arrays will provide two key benefits:

- Our electrode arrays cover a larger area than commercially available arrays, extending from the midthoracic to the sacral extents of the spinal cord. It is possible that the optimal stimulation sites for facilitating stepping versus standing may be spatially distinct on the spinal cord. If this is the case, conventional arrays are less likely to be able to recover both stepping and standing in the same patient.

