These individuals will not be concurrently enrolled in any other experimental studies unless approved by the principal investigator. Each research participant will be given a coded identification number to designate all evaluations. We will retain the data for reporting to granting agencies even when the individual is not eligible for the study. This data will be stored by the coded identification number without information identifying the individual.

We will evaluate the research participants for: 1) functional neurophysiological assessment (FNPA); 2) somatosensory evoked potentials (SEP); 3) sympathetic skin responses (SSR); 4) efferent motor activity during standing; 5) efferent motor activity during stepping; 6) reflexes during supine, prone, sitting and standing; 7) bladder function; and 8) cardiovascular function. Each of these measurements will take between 1 and 4 hours. The FNPA, SEP and SSR will be performed while the research participant is lying supine on a mat. The efferent motor assessments will be performed in the body weight support treadmill with the assistance of trainers at the hip and at each leg.

We will assess metabolic parameters, inflammatory markers, complete blood count, bone density and health markers, blood glucose control and drug toxicity panel. A trained

technician will draw a venous blood sample. Participants may undergo a 12-hour fast the night before, including no food or drink including alcohol or caffeine (water is permitted). A comprehensive drug screen by urinalysis will be done to assess the use of illicit drugs. These blood and urine analyses may be repeated periodically throughout the course of the study. A blood sample will be stored for batch processing at the end of the study (for participants that complete the screening process).

After completion of these evaluations, participants will undergo 80 sessions of step/stand training. We will repeat experiments after the completion of the 80 training sessions to quantify that no motor pattern changes are achievable with locomotor training alone. Drs. [name], [name] and [name] will meet to discuss the results of the preliminary testing and evaluate if the participant is eligible for surgical implantation for SCES.

FULL ENROLLMENT: Surgery + Epidural Stimulation + Training (2nd consent)

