These results will reveal whether conventional electrodes can be used to facilitate stepping in clinically complete spinal cord injury patients. This study will clarify whether the optimal spinal cord sites for using epidural stimulation to induce stepping and standing migrate over the course of training in the human spinal cord. We expect that these data will provide further evidence of the plasticity of the injured spinal cord, and that training modifies the spinal networks for stepping. Stepping performance of the patients will be compared against historical controls that were given step training without epidural stimulation. The criteria for success of the combined treatment will be determined by the best outcomes that have been obtained for previous patients who were only trained.

h. Treatment regimen(s) (*for medically invasive research*)

i. Clinical information (when applicable) (*for medically invasive research*)

j. Statistical analysis of the collected data

No statistical analysis will be used for comparison of data. This study is designed as a proof of principle study without statistical power to demonstrate the feasibility of the methods.

k. Data and Safety Monitoring Plan

Entity responsible for monitoring is identified:

The study will be monitored by a Data Safety Monitoring Board consisting of: [name] (Neurosurgeon), [name] (physiatrist); [name]

[name] (cardiologist) and [name] (Urologist) who are not associated with the study.

Policies and procedures for adverse event reporting are described:

If a subject develops an adverse event it will be reported to the DSMB, local IRB and Sponsor within 24 – 48 hours of being notified of the event.

Protocol Compliance:

Any deviations in the protocol will be documented and reported to the IRB.

Plans for measuring appropriate intervals between safety reviews and predetermined criteria for stopping the study:

Research participants will be continuously monitored for complications, adverse events and/or serious adverse events. If any complications arise during the course of the study the local Medical Advisor ([name]) will be notified. All study procedures will be halted until the complication, adverse event and/or serious adverse event has been reviewed by the medical advisor and it has been determined that it is safe for the study participant to return to participating in study procedures.

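### The stated purpose is feasibility of the methods, but the only success rule is a best-performer rule with no denominator, which cannot support a feasibility conclusion beyond 'possible in at least one person'

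*Protocol*

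**What the plan says.** **Purpose.** Section j: "This study is designed as a proof of principle study without statistical power to demonstrate the feasibility of the methods". The sentence before it reads: "No statistical analysis will be used for comparison of data".

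**Success rule.** Section A (Background) sets the benchmark: "historical controls will consist of the best stepping and standing performance that have been observed previously in our laboratory". It then says: "Performance beyond this threshold by any individual treated with both epidural stimulation and training will be interpreted as a significantly better intervention than training alone". The closing paragraph of section G restates the criterion without mentioning a single individual: "The criteria for success of the combined treatment will be determined by the best outcomes that have been obtained for previous patients", meaning those who had training only.

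**Route to treatment.** Section D (Screening) places 80 training sessions under a first consent and warns that entry does not guarantee surgery. After those sessions the investigators meet to discuss the results and "evaluate if the participant is eligible for surgical implantation for SCES". A second consent follows. Under section G, Stage 1A, persistent MRSA colonisation leads to exclusion. Stage 1B accepts that infection may require removal of the electrodes. Stage 2A then plans 160 sessions at five per week.

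**Sample size.** Section A attaches 10 to people who will be implanted. Section F attaches it to people recruited over ten years. Section G (Locomotor Training Intervention) attaches it to people in the 80 sessions.

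**The concern.** Feasibility of the methods and a performance record are different findings. A record depends on the best participant. Feasibility, on any reading wider than one success, depends on what happened to everyone who entered. The protocol foresees loss at several steps, but its only rule for a favourable conclusion does not register that loss.

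The study is meant to inform a second-phase electrode array. If its results are carried forward as showing that the methods are feasible, that claim would rest on the best case among participants who passed several selections. With 10 attached to three groups, a reader could not tell what any reported proportion was a proportion of.

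**Working it through.** **1. Is there another criterion?** The candidates elsewhere in the protocol are not study-level rules:
- The hope in section F that participants might stand or walk with an aid is an expectation.
- The progression criterion in section D (Locomotor Training) decides whether a session counts.
- Repeat testing after the 80 sessions sets no success threshold.

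The best-performer rule stands alone. The 10 has no stated derivation, so there is no sample-size figure to reproduce.

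**2. The least that meets the rule.** One of 10. The exact limits for x of n are the 2.5% point of Beta(x, n−x+1) and the 97.5% point of Beta(x+1, n−x). For 1/10 this gives 0.3% to 44.5%.

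**3. Why the denominator matters.** Suppose 8 people complete. The 8, and the 14 and 20 starters below, are assumptions; the protocol gives none of them.

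| Denominator | Proportion | Exact 95% interval |
|---|---|---|
| 8 of 10 implanted | 80% | 44% to 97% |
| 8 of 14 starters | 57% | 29% to 82% |
| 8 of 20 starters | 40% | 19% to 64% |

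The same eight people give 80% or 40%, depending on which group the denominator is.

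**4. How often the rule could be met alongside poor completion.** Let c be the chance that a participant completes and r the chance that a completer exceeds the historical best. Assume independence and that only completers can set a record. Then

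P(rule met and at most 4 of 10 complete) = Σ(k=0 to 4) C(10,k) c^k (1−c)^(10−k) [1 − (1−r)^k].

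| c | r = 0.2 | r = 0.5 |
|---|---|---|
| 0.3 | 0.357 | 0.657 |
| 0.4 | 0.305 | 0.534 |
| 0.5 | 0.196 | 0.333 |

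Both c and r are assumptions. The table shows what the rule permits, not what is expected.

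**5. Is the rule wholly insensitive to loss?** No. Fewer people treated means fewer chances of a record. If each treated person has a 0.2 chance, the rule is met with probability 1 − 0.8^10 = 0.89 with 10 treated and 1 − 0.8^4 = 0.59 with 4. Loss lowers the chance of meeting the rule, but once the rule is met, nothing in it records the loss.

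**6. Completion window.** At five sessions a week, 160 sessions take 160/5 = 32 weeks, or about 32/4.345 = 7.4 months. Section D (Full Enrollment) gives this stage six to eight months and section G, Stage 2A, gives four to eight. The two must be reconciled before 'completed on time' can be counted.

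**The case against.** The best reply is that section j says proof of principle. In such a study, feasibility can mean that the effect can be obtained at all, and a performance criterion fits that. The objectives in section B are to improve standing and stepping and to inform electrode design; retention and uptake are not among them. This stands. A reader might take the protocol's question to be whether the whole programme can be delivered, but that is only one reading of section j. The sentence can even be parsed as saying that the study lacks power to show feasibility. On either reading, section j does not say what a record would and would not establish.

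Second, a reader might infer that the plan declares the study a success if one participant sets a record while the other nine withdraw or are explanted. The documents do not support that. The rule speaks of the intervention and the combined treatment, not of the study or of feasibility. Section k also provides a monitoring board and stops all study procedures after a serious adverse event related to the study product. These safeguards limit the explant scenario. They do not count withdrawals or people never implanted, and they do not alter the rule.

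Third, disposition tables are usually left to a statistical analysis plan, which may exist. Their absence alone would be no finding. The point here is the success rule that the protocol itself fixes.

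Fourth, the 80 sessions are screening. Someone not implanted because training alone helped is screening working as intended. This also stands, and the reporting must separate such losses from failures.

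**Conclusion.** The point holds in limited form. The best-performer rule in section A, echoed at the end of section G, has no denominator and can be met by one person in 10. It cannot carry a feasibility conclusion beyond 'possible in at least one person'. Because 10 refers to implanted, recruited and trained participants in different places, no proportion has a fixed base.

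The 0.3% to 44.5% interval for 1 of 10 and the three meanings of 10 follow from the document. The spread from 80% to 40% and the joint probabilities of 0.20 to 0.66 rest on assumed completion, record and starter figures. Nothing in the protocol says that loss will be heavy. This limits what may be concluded and is worth correcting; it does not invalidate the study.

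**What to change.** In section j:

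1. State that a record by one individual shows only that the effect is possible and is not evidence of feasibility. Cross-refer this to the sentence in section A, so that the any-individual rule does not stand unqualified.
2. Report the number exceeding the historical best over all implanted and over all who started the 80 sessions.
3. Report feasibility as counts by stage with exact (Clopper-Pearson) 95% intervals: starters, accepted for implant, implanted, completed the 160 stimulated sessions, and device status and device-related serious adverse events at three years.
4. Give reasons for loss, separating ineligibility by design (for example a response to training alone) from withdrawal or failure, and give device removals by reason.
5. State which group the 10 refers to, and reconcile the two stage lengths before using either as a completion window. Define completion with regard to sessions that do not count and sessions limited by the physician.

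These are descriptive counts, so they do not conflict with the exclusion of statistical comparison. The material is already provided for: data on ineligible people are retained, sessions are counted, follow-up runs three years after surgery, and adverse events are reported. No new participants are needed.

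The cost is some added text, a few definitions and a little more tabulation. Reported rates will look less favourable than rates among implanted completers, and intervals will be wide: even 10 of 10 has a lower limit of 0.025^(1/10) = 69%. The change sets no pass mark. If the sponsor wants one, it has to be chosen in advance.
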